13.4.1.2. Treatment Control Group

Endpoint	Day 0 Visit Parent Study	Day 0 Visit BEL116027 Study [1]	Week 24 Visit	Week 52/ Exit Visit	Week 16 Follow -up Visit				
		Baseline							
Flare, PGA, Prednisone, SLICC	N/A	52-Week Trea	atment Phase	Maintenance Phase	N/A				
Baseline									
SS, Auto-antibodies Immunoglobulins, B-cells [2], BLyS	Pre-Study Phase	52-Week Trea	atment Phase	Maintenance Phase	N/A				
		Baseline		•					
Rebound [3]		52-Week Trea	atment Phase						
	Pre-Study Phase	First 24 Weeks	N/A	N/A	N/A				
		Baseline		•					
Adverse Events, Lab Parameters, Vital Signs, Con Meds, Immunogenicity [2]	N/A	52-Week Trea	atment Phase	Maintenance Phase	N/A				

N/A = Not Applicable.

[1] If the first infusion date differs from the Day 0 visit date, then the first infusion date will be used as the phase cut-point.

[2] Immunogenicity and B-cells may also be collected at the 6-month follow-up visit. The 6-month follow-up visit is not represented in the diagram since it does not define a treatment phase of the study.

[3] Rebound is only assessed up to the Week 24 visit.

13.4.1.3. Long-term Discontinuation Group

Endpoint	Day 0 Visit Parent Study	Day 0 Visit BEL116027 Study	Week 2	24 Visit	Week 52/ Exit Visit			
		Baseline						
Flare, PGA, Prednisone, SLICC	N/A	N/A	52-Week Pha	Treatment ase	N/A			
Baseline								
SS, Auto-antibodies Immunoglobulins, BLyS	N/A	Pre-Study Phase	52-Week Treatment Phase		N/A			
		Baseline						
Rebound	N/A	Pre-Study Phase	52-Week Pha	Treatment ase	N/A			
	N/A	FIE-Sludy Fildse	First 24 Weeks	N/A				
		Baseline						
Adverse Events, Lab Parameters, Vital Signs, Con Meds	N/A	N/A	52-Week Treatment Phase		N/A			

N/A = Not Applicable.

Treatment State	Treatment Group	Definition
Treatment Emergent	TH, LTD	AE Onset Date ≥ Day 0 visit date
Treatment Emergent	TC	AE Onset Date ≥ Date of First Infusion in BEL116027
Onset Time Since 1 st Dose (Days)	TH, TC	If Date of First Infusion in BEL116027> AE Onset Date: = AE Onset Date - Date of First Infusion in BEL116027 If Date of First Infusion in BEL116027≤ AE Onset Date = AE Onset Date - Date of First Infusion in BEL116027+1 =Missing otherwise.
Onset Time Since Study Start (Days)	TH, TC, LTD	If Day 0 visit date > AE Onset Date: = AE Onset Date – Day 0 visit date If Day 0 visit date ≤ AE Onset Date = AE Onset Date - Day 0 visit date +1 =Missing otherwise.
Duration (Days)	TH, TC, LTD	AE Resolution Date – AE Onset Date + 1
Drug-related	TH, TC, LTD	If relationship is marked 'YES' on Inform/CRF OR value is missing.

1. NOTES:

• If the AE Onset date is missing, then the AE will be considered as treatment emergent.

13.5. Appendix 5: Data Display Standards & Handling Conventions

13.5.1. Reporting Process

Software

Soltwale		
The currently supported versions of SAS software will be used.		
Reporting Area		
HARP Server	US1SALX00259	
HARP Compound	GSK1550188/BEL116027/final_01	
and Reporting effort		
Analysis Datasets		
 Analysis datasets will be created according to CDISC standards (SDTM IG Version 3.2 & ADaM IG Version 1.0). 		
Generation of RTF Files		
RTF files will be generated for all tables in the final_cdisc RE		

13.5.2. Reporting Standards

General

The current GSK Integrated Data Standards Library (IDSL) will be applied for reporting, unless
otherwise stated (IDSL Standards Location: https://spope.gsk.com/sites/IDSLLibrary/SitePages/Home.aspx):

- 4.03 to 4.23: General Principles
- 5.01 to 5.08: Principles Related to Data Listings
- 6.01 to 6.11: Principles Related to Summary Tables
- 7.01 to 7.13: Principles Related to Graphics
- Do not include subject level listings in the main body of the GSK Clinical Study Report. All subject level listings should be located in the modular appendices as ICH or non-ICH listings

Formats

- GSK IDSL Statistical Principles (5.03 & 6.06.3) for decimal places (DP's) will be adopted for reporting of data based on the raw data collected, unless otherwise stated.
- Numeric data will be reported at the precision collected on the eCRF.
- The reported precision from non eCRF sources will follow the IDSL statistical principles but may be adjusted to a clinically interpretable number of DP's.

Planned and Actual Time

- Reporting for tables, figures and formal statistical analyses:
 - Planned time relative to dosing will be used in figures, summaries, statistical analyses and calculation of any derived parameters, unless otherwise stated.
 - The impact of any major deviation from the planned assessment times and/or scheduled visit days on the analyses and interpretation of the results will be assessed as appropriate.
- Reporting for Data Listings:
 - Planned and actual time relative to study agent dosing will be shown in listings (Refer to IDSL Statistical Principle 5.05.1).

• Unscheduled or unplanned readings will be presented within the subject's listings.

Unscheduled Visits

- Unscheduled visits will not be included in summary tables.
- Unscheduled visits will be included in figures unless their inclusion contributes adversely to

visual presentation or interpretation of the figure.		
All unscheduled visits will be included in listings.		
Descriptive Summary Statistics		
Continuous Data	Refer to IDSL Statistical Principle 6.06.1	
Categorical Data	N, n, frequency, %	
Graphical Displays		
Refer to IDSL Statistical Principals 7.01 to 7.13.		

13.5.3. Reporting Standards for Pharmacokinetic

Pharmacokinetic Concentration Data		
Descriptive Summary Statistics (Log Transformed)	 N, n, geometric mean, 95% CI of geometric mean, standard deviation (SD) of log transformed data and between geometric coefficient of variation (CVb (%)) will be reported. CV_b (%) = √ (exp(SD²) - 1) * 100 (SD = SD of log transformed data) 	
Parameters Not Being Log Transformed	N, n mean, 95% CI, standard deviation (SD), median, 25 th and 75 th percentile, minimum and maximum will be reported.	
Pharmacokinetic Parameter Data		
Is NQ impacted PK Parameters Rule Being Followed	Yes, refer to Standards for Handling NQ Impacted PK Parameters	

13.6. Appendix 6: Derived and Transformed Data

13.6.1. General

Multiple Measurements at One Time Point

- Mean of the measurements will be calculated and used in any derivation of summary statistics but if listed, all data will be presented.
- Subjects having both High and Low values for Normal Ranges at any post-baseline visits for safety parameters will be counted in both the High and Low categories of "Any visit post-baseline" row of related summary tables. This will also be applicable to relevant Potential Clinical Importance summary tables.

Study Day

- Calculated as the number of days from the Day 0 Visit Date (i.e., Day 1) to the assessment date or visit date of interest (Ref Date)
 - Ref Date = Missing \rightarrow Study Day = Missing
 - Ref Date < Day 0 Visit Date \rightarrow Study Day = Ref Date Day 0 Visit Date
 - Ref Data ≥Day 0 Visit Date → Study Day = Ref Date –Day 0 Visit Date + 1

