4.4. Withdrawal Criteria

A subject may voluntarily discontinue participation in this study at any time or may be withdrawn at the discretion of the investigator. Record the primary reason for withdrawal in the electronic case report form (eCRF).

Subjects in the treatment holiday and control groups will be withdrawn from the study for:

- Pregnancy: positive urine pregnancy test.
- Clinically significant, potentially life-threatening (Grade 4) AE that in the clinical judgement of the investigator is possibly, probably or definitely related to belimumab.
- Liver chemistry abnormalities. Refer to details regarding liver chemistry abnormalities and withdrawal as specified in Section 6.4.1.

- Laboratory parameters: Demonstrate clinically important changes in laboratory parameters.
- Prohibited concurrent medication or therapy.

These subjects will complete the Week 52 Exit visit (except for dosing with belimumab) at the time of discontinuation and the16-week follow-up visit assessments at least 16 weeks after the withdrawal visit or last dose of belimumab as appropriate (see Section 6). The 6 month follow-up visit is scheduled only for those subjects in the treatment holiday or control groups.

Subjects in the long-term discontinuation group will be withdrawn from the study for:

- Pregnancy: positive urine pregnancy test.
- Laboratory parameters: Demonstrate clinically important changes in laboratory parameters.
- Have developed clinical evidence of significant, unstable or uncontrolled, acute or chronic diseases not due to SLE (i.e., cardiovascular, pulmonary, hematologic, gastrointestinal, hepatic, renal, neurological, malignancy or infectious diseases), or experienced an adverse event (AE) that could, in the opinion of the principal investigator, put the subject at undue risk.
- Have developed any other medical diseases (e.g., cardiopulmonary), laboratory abnormalities, or conditions (e.g., poor venous access) that, in the opinion of the principal investigator, makes the subject unsuitable for the study.

These subjects will complete the Week 52 visit assessments (see Section 6).

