6. STUDY ASSESSMENTS AND PROCEDURES

All subjects will attend clinic visits for efficacy and safety assessments every 4weeks for 52 weeks (see Table 2).

Subjects in the treatment holiday and control groups will be dosed with belimumab at the Week 52 visit in Table 2 only if they are continuing belimumab therapy in the maintenance phase of this study. Subjects in the treatment holiday and control groups who wish to continue belimumab therapy after the Week 52 visit, will proceed to the Week 4 visit in Table 3 (Time and Events Table for additional years) and continue to cycle through clinic visits from Week 4 through Week 48 in Table 3 on an annual basis (see Section 3.1). Subjects in the treatment holiday and control groups who do not wish to continue belimumab therapy after Week 48 will proceed to the Week 52 (Exit) visit but will not be dosed with belimumab.

Subjects in the treatment holiday and control groups who meet the protocol-defined withdrawal criteria specified in Section 4.4 at any time during Year 1 or the additional years will undergo assessments scheduled at the Exit visit (Week 52) in Table 2 except for dosing with belimumab. At approximately 16 weeks after the withdrawal visit or the last dose of belimumab as appropriate, these subjects will also undergo the assessments scheduled at the 16-week follow-up visit; the 6 month follow-up visit is scheduled only for these discontinued subjects in the treatment holiday or control groups.

Subjects in the long-term discontinuation group will attend for clinic visits from Day 0 through Week 52 in Table 2 only. The 16-week and 6-month follow-up visits do not apply to this group. Subjects in the long-term discontinuation group who meet the protocol-defined withdrawal criteria specified in Section 4.4 at any time during Year 1 will undergo assessments scheduled at the Exit visit (Week 52) in Table 2.

2012N154810_06

CONFIDENTIAL

2018N381035_00 BEL116027

Table 2Time and Events Table (Year 1)

	Screen	Treatment Holiday Study												Follow-up			
Visit	1	2	3	4	5	6	7	8	9	10	11	12	13	14	15		
Study Day	Up to -30 ¹	0 ²	28 ±7d	56 ±7d	84 ±7d	112 ±7d	140± 7d	168 ±7d	196± 7d	224 ±7d	252 ±7d	280± 7d	308 ±7d	336 ±7d	364 ±7d or Exit	16-wk ±7d ³	6 mo ±7d
Study Week		0	4	8	12	16	20	24	28	32	36	40	44	48	52		
Written Informed Consent ⁴	Х																
Demography		Х															
Medical History		Х															
SLE History		Х															
Therapy History		Х															

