7.2.4.2. Rebound and SELENA SLEDAI Scores

Missing data will be imputed using the principle of Last Observation Carried Forward (LOCF). For the TH group, LOCF will not be applied across the TH and RS phases. If an individual SS item data is missing at the first timepoint in the RS phase, the item will be considered not present.

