13.3.3. Analysis Visit and Analysis Visit Number

The data are analyzed according to the planned visit assignment in the data.

Exit/withdrawal visits must be slotted to the appropriate planned visit according to the study phase. This will only be done for subjects that withdrew early and did not complete the 52-week treatment phase. Unscheduled laboratory visits will also be slotted to the appropriate planned visit.

The Analysis Visit is assigned based on the interval in which the Study Day for the exit/withdrawal visit or unscheduled laboratory visit falls according to intervals (inclusive) provided below. For completeness, the table also includes visits which are not slotted; these visits will have 'na' for 'not available' listed for the Interval Start and End Day.

	Analysis		Interval Start Day	Interval End Day
Analysis Visit	Visit Number	Target Study Day ¹		_
Screening	10	-34	na	na
52-week Treatment	Phase visits:			
Baseline	20	1	na	na
Week 4	30	29	22	42
Week 8	40	57	43	70
Week 12	50	85	71	98
Week 16	60	113	99	126
Week 20	70	141	127	154
Week 24	80	169	155	182
Week 28	90	197	183	210
Week 32	100	225	211	238
Week 36	110	253	239	266
Week 40	120	281	267	294
Week 44	130	309	295	322
Week 48	140	337	323	350
Week 52	150	365	351	378

	Analysis		Interval Start Day	Interval End Day				
Analysis Visit	Visit Number	Target Study Day ¹						
¹ Day 0 visit date in study 116027 = Study Day 1.								

13.3.4. Windows for Assessment of Post-injection/infusion sensitivity reactions (PISR) and hypersensitivity reactions (HSR)

The windows for assessment of PISR/HSR, as described in the AESI definitions in Section 13.9.2, are as follows:

Date of Infusion								
Day 1	Day 2	Day 3						
SMQ narrow, broad and algorithmic searches (On day of injection/infusion or within 3								
days of injection/infusion)								

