13.7. Appendix 7: Reporting Standards for Missing Data

13.7.1. Premature Withdrawals

Element	Reporting Detail
General	Subject study completion (i.e. as specified in the protocol) was defined as s
	• Treatment holiday group: completion of the 24-week treatment holiday period plus the belimumab re-introduction treatment period to Week 52.
	• Control and long-term discontinuation groups: completion of all visits to Week 52.
	For reporting purposes, withdrawal from the maintenance phase is defined in Section 13.6.2.
	Withdrawn subjects were not replaced in the study
	All available data from participants who were withdrawn from the study will be listed and all available planned data will be included in summary tables and figures, unless otherwise specified.
	Withdrawal visits will be slotted as per Appendix 3: Assessment Windows or will be summarised as withdrawal visits.

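### Exit visits are slotted by study day into windows that may already hold an attended visit, and the only rule for several values is the mean, so change seen at withdrawal can be diluted in by-visit SELENA SLEDAI, PGA and rebound results

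*SAP*

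**What the plan says.** **Slotting.** SAP 13.3.3 says of subjects who leave before completing the 52-week phase: "Exit/withdrawal visits must be slotted to the appropriate planned visit according to the study phase". The slot depends on timing only: "The Analysis Visit is assigned based on the interval in which the Study Day for the exit/withdrawal visit or unscheduled laboratory visit falls". Nothing limits this to a planned visit that was missed. The Week 12 row reads "Week 12 50 85 71 98", that is, visit number 50, target Day 85, window Days 71 to 98.

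**Timing of the exit visit.** For the holiday and control groups, Protocol 4.4 states: "These subjects will complete the Week 52 Exit visit (except for dosing with belimumab) at the time of discontinuation". That is not tied to the four-weekly schedule. Protocol Section 6 also sends withdrawing long-term discontinuation subjects to the Exit assessments.

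**Several values.** SAP 13.6.1, under the heading Multiple Measurements at One Time Point, gives one rule: "Mean of the measurements will be calculated and used in any derivation of summary statistics but if listed, all data will be presented". No latest, closest or worst-record rule appears.

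**Use of the values.** SELENA SLEDAI and PGA are summarised as change from baseline at each visit (SAP 7.2.2.4, 7.3.1.1). Rebound is a score in the first 24 weeks above the parent-study baseline, shown by visit and at any time (7.2.1.3, 7.2.2.3). All three use LOCF, which in the holiday group stops at the boundary between the holiday and re-start phases (7.2.4.2, 7.3.4.1).

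**A second option.** SAP 13.7.1 adds: "Withdrawal visits will be slotted as per Appendix 3: Assessment Windows or will be summarised as withdrawal visits".

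**The concern.** A subject can attend a planned visit, worsen and exit within the same window. Two records then carry one visit label, and the only stated way to reduce them to one value is to average them.

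The two records are not replicates. SELENA SLEDAI covers the visit and the 10 days before it, so scores from Day 85 and Day 97 describe separate periods. Averaging mixes the state before the change with the state at withdrawal. Some exits can be tied to worsening disease: holiday and control subjects who start a prohibited therapy must be withdrawn (Protocol 5.5.2).

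At stake are a secondary endpoint (SELENA SLEDAI change), an exploratory one (PGA change) and rebound. Rebound is part of the study's stated purpose, and its table (SAP 13.11.5, Table 2.6) is marked for the headline package. SAP 13.6.1 protects extremes for safety ranges by counting a subject as both high and low, but gives rebound no such protection.

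**Working it through.** The plan gives no figure to reproduce, so the check applies its own windows and rules.

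**Inputs**
- Windows (SAP 13.3.3): for target day T, Weeks 8 to 52 run from T−14 to T+13. For Week 12, 85 − 71 = 14 and 98 − 85 = 13. Week 4 runs from T−7 to T+13.
- Visits every 28 days (Protocol Section 6), each allowed ±7 days (Protocol Table 2).
- Mean rule from SAP 13.6.1, taking one analysis window as one time point. This is a reading of the text.
- Assumed, not in the documents: exits spread evenly over the days between visits, and all example scores.

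**Step 1: how often an exit shares the window of the visit just attended**

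| Visits | Week 12 held | Next visit due | Possible exit days | Days inside the Week 12 window | Share |
|---|---|---|---|---|---|
| On target | 85 | 113 | 86–112 (27) | 86–98 (13) | 13/27 = 48% |
| All 7 days early | 78 | 106 | 79–105 (27) | 79–98 (20) | 20/27 = 74% |
| All 7 days late | 92 | 120 | 93–119 (27) | 93–98 (6) | 6/27 = 22% |

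The remaining days fall in the empty Week 16 window, so nothing is averaged. The counts are the same after every visit from Week 4, because each window ends at T+13. Exits on Study Days 2 to 21 have no window at all, which is a separate small gap.

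**Step 2: change since the earlier visit.** With earlier score p and exit score e, the mean is (p + e)/2, and (p + e)/2 − p = (e − p)/2. The step is exactly halved.

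**Step 3: change from baseline.** With baseline B, the reported change is (p + e)/2 − B instead of e − B. It is halved only when p = B.
- SELENA SLEDAI, B = 10 (parent study), p = 4, e = 12: the mean is 8, so the change is −2 instead of +2.
- PGA, Day 0 = 0.5, p = 0.8, e = 2.0: the mean is 1.4, so the change is +0.9 instead of +1.5.

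**Step 4: rebound.** On the mean, rebound needs (p + e)/2 > B, that is, e > 2B − p. With B = 10 and p = 4, the exit score must exceed 16 instead of 10. A score of 12 is a rebound on its own value and not on the mean.

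**Step 5: carry-forward.** If LOCF acts on the by-visit value, the example carries 8 instead of 12. For a control or long-term discontinuation subject this could run to Week 52. For a holiday-phase exit it can go no further than Week 24.

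**Step 6: weight of one subject.** SAP 2.3 reports 12 holiday and 39 long-term discontinuation subjects enrolled. One missed rebound moves the any-time rate by 1/12 = 8.3 or 1/39 = 2.6 percentage points.

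**The case against.** The strongest reply is that the SAP never states this averaging. The mean rule concerns one time point, and 13.3.3 only assigns a label, so two dates in one window need not be one time point. SAP 13.7.1 also allows withdrawal visits to be summarised separately, in which case nothing collides. This has force: the averaging follows from combining two rules. It does not remove the problem. No other rule is given, so a programmer must apply the mean or invent one, and 13.7.1 leaves open a choice that 13.3.3 treats as settled.

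Further points that stand:
- Rebound is binary and defined on a single score. Its any-time row may already use individual scores, and the mean rule speaks of summary statistics.
- SAP 13.7.2 carries the last non-missing assessment, which may be read as the exit score itself.
- If the exit coincides with a scheduled visit, there is only one record.
- The listings show every value, results are descriptive only, and time to first SFI flare uses event dates.

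A reader might infer that the bias falls mainly on the off-drug groups. The documents do not show this. Holiday subjects who worsen before Week 24 can escape to maintenance, and that visit keeps its own label (SAP 13.3.1). Worsening SLE is not a listed withdrawal criterion for the long-term discontinuation group. Control subjects must also leave on starting prohibited therapy.

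**Conclusion.** The concern holds as a conflict between stated rules with a real effect, limited to particular exits and endpoints. If one window counts as one time point, an exit soon after an attended visit is averaged with it. This applies to about 48% of possible exit days with on-target visits and evenly spread exits, and 22% to 74% when all visits shift by 7 days. In those cases the change since the earlier visit is halved in the by-visit SELENA SLEDAI and PGA summaries. A rebound can be lost from the by-visit row, and from the any-time row if that is derived from by-visit values. The mean may also be carried forward within the phase, because the SAP does not say which value LOCF takes.

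Three stronger readings are tempting and not supported. Worsening at withdrawal is not halved throughout: change from parent-study baseline is halved only when the earlier score equals that baseline, and rebound is missed rather than halved. A Week 12 value in the holiday group is not carried to Week 52. A mainly off-drug bias is not shown. The primary endpoint and Escape visits are untouched. The documents do not give the number of early exits, so the number of subjects affected is unknown.

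**What to change.** - In SAP 13.6.1, limit averaging to replicates taken on the same date.
- In SAP 13.3.3, state that when a planned and an exit record share a window, the exit (latest) record supplies the by-visit value and is the one LOCF carries. Repeat the LOCF part in 7.2.4.2 and 7.3.4.1.
- In SAP 7.2.2.3, derive rebound, by visit and at any time, from each visit's own score before any averaging.
- In SAP 13.7.1, remove the choice between slotting and separate summary so that it agrees with 13.3.3.

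The cost is a few sentences and one record-selection step in the analysis datasets, with no new data. The downside is that a single exit value is slightly noisier than an average of two.

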13.6.2. Study Population

Demographics

Study Phases Definitions for Disposition

- Completion/withdrawal for the 52-Week Treatment Phase will be derived as follows:
 - Withdrawn if the subject completion status is marked as No and the subject has no visits during the maintenance phase.
 - Complete if the subject completion status is marked as Yes and the subject has no visits during the maintenance phase.
- Completion/withdrawal for the Maintenance Phase will be derived as follows:
 - Withdrawn if the subject completion status is marked as No and the subject has at least one visit during the maintenance phase.
 - Complete if the subject completion status is marked as Yes and the subject has at least one visit during the maintenance phase.

Age

- GSK standard IDSL algorithms will be used for calculating age where birth date will be imputed as follows:
 - Any subject with a missing day will have this imputed as day '15'.
 - Any subject with a missing date and month will have this imputed as '30th June'.
- Birth date will be presented in listings as 'YYYY'.
- Analysis age is derived in years relative to the Day 0 visit date, and is calculated in SAS as follows:

Analysis Age (years) INTCK('year', Date of Birth, Day 0 Date)

- (MONTH(Day 0 Date) < MONTH(Date of Birth)

Demographics

or (MONTH(Day 0 Date) eq MONTH(Date of Birth)

and $DAY(Day \ 0 \ Date) < DAY(Date \ of \ Birth)$)

Proteinuria

- For analysis, urine protein in g/24-hour will be approximated by the urine protein:creatinine ratio (uPCR).
- The value for reporting and analysis is stored in the uPCR result variable corresponding to the
 original unit in the SI dataset. Depending on the study, units for uPCR may be reported in g/g or
 mg/mg. As long as the units are the same in the numerator and denominator, the ratio will be
 the same.
- The SI dataset standard unit is reported in mg/mmol is not used for reporting and analysis purposes in this study.

Concomitant medications

- Concomitant medications are defined as
 - a. Medications that start on or before the Day 0 visit date and end on or after the Day 0 visit date, or
 - b. Medications that start after the Day 0 visit date
- Medications that meet criterion 'a' are considered to be in use at baseline.
- Medications will be assigned to the 52-week treatment or maintenance phases, as per the definitions in Section 13.4.1.
- Medications with partial or missing start and/or stop dates will be assumed to be concomitant
 unless there is evidence through comparison of partial dates to suggest otherwise, for example
 if the day is missing, then the month and year will be compared to the month and year of the
 first dose date of study treatment and if the month and year are the same or later, then the
 medication will be considered concomitant.

Allowable SLE Medications at Baseline

There are 5 medication categories that are evaluated. These medication categories are defined in the table below and stored in the variable CMSCAT. Only medications providing systemic exposure are evaluated. Systemic exposure is based on the route of administration. A flag variable for systemic exposure when CMSCAT is not blank is defined below and stored in the variable SYSTEMIC. The medication must have one of the defined medication categories below (CMSCAT ne blank) and must provide systemic exposure (SYSTEMIC='Y').

Medication Category (CMSCAT)	Rule
Anti-malarials	Set CMSCAT to "ANTIMALARIALS" if the preferred term begins with "QUINACRINE", "QUININE", "HYDROXYCHLOROQUINE", "MEPACRINE", or "CHLOROQUINE"
Steroids	Set CMSCAT to 'STEROIDS' if at least one associated ATC code (ATCCD1 – ATCCD6) begins with 'H02'

Allowable SLE Medications at Baseline	
Immunosuppressants	Set CMSCAT to 'IMMUNOSUPPRESSANTS' if at least one associated ATC code (ATCCD1 – ATCCD6) begins with 'L04A' or the preferred term begins with "CYCLOPHOSPHAMIDE" or "MERCAPTOPURINE".
NSAIDs	Set CMSCAT to NSAIDs if at least one associated ATC code (ATCCD1 – ATCCD6) begins with 'M01A'.
Aspirin	Set CMSCAT to "ASPIRIN" if CMDECOD contains "ACETYLSALICYLIC ACID" or "ACETYLSALICYLATE LYSINE".
Prohibited	Set to "PROHIBITED" if any of the following conditions are met, if CMDECOD equals "INVESTIGATIONAL DRUG", "IMMUNOGLOBULIN", "ADALIMUMAB", "ETANERCEPT", "INFLIXIMAB", "RITUXIMAB", "ABATACEPT", "ANAKINRA", "GOLIMUMAB", "CERTOLIZUMAB" and/or A review of the surgeries/procedures form indicates the subject had "PLASMAPHERESIS".
Traditional Chinese medications Glycosides of Paeony and Tripterygium	These medications will be identified based on a clinical review of all the concomitant medications assigned the following drug collection codes in the GSK drug dictionary: 50119401, 54654601, 40987301, 50192401, 53020201, 53060901, 53766001, 53927401, 53959101, 53959201, 53990601, 54619401, 54731901, 54908201, 59164101
Systemic (SYSTEMIC)	Rule
Blank	If CMSCAT=blank
Y	'Y' if CMSCAT ne blank and the route of administration is "INTRADERMAL" "PO" "INTRAMUSCULAR", "INTRAVENOUS", "ORAL", or "SUBCUTANEOUS"
Ν	'N' otherwise and CSMCAT ne blank

Treatment Compliance

• Treatment compliance for patients completing the 52 week treatment phase or withdrawals is calculated as:

treatment compliance (%)

- $= 100 \times \frac{Number \ of \ infusions \ prescribed Number \ of \ infusions \ missed}{Number \ of \ infusions \ prescribed}$
- Prescribed number of infusions will be 7 for the TH arm and 13 for the TC arm, except for TH subjects who escape to the Maintenance Phase. For TH subjects who escape, the treatment compliance will be missing. The Week 52 infusion is considered to be the first infusion of the maintenance phase.
- NB: for withdrawals the number of infusions prescribed is the number from Day 0 up to the withdrawal date

Extent of Exposure

Number of days of exposure to study treatment during the 52-week Treatment Phase will be calculated based on the formula:

Duration of Exposure in Days = (Date of last infusion in BEL116027 52-week treatment Phase– Date of first infusion in BEL116027) + 28

- The Week 52 infusion is considered to be the first infusion in the Maintenance Phase, and will not be considered in this calculation.
- Subjects who were enrolled in the TH and TC groups but did not receive an infusion will be categorised as having zero days of exposure.
- Exposure will not be calculated for the LTD group.
- Only complete dates will be used when calculating duration of exposure.
- Exposure will not be adjusted for skipped infusions.

